3.3.1.1. COVID-19 Vaccination During the Study

It is recommended for patients to complete COVID-19 vaccination at least 14 days prior to receiving the first dose of ISA101b or to delay COVID-19 vaccination until at least 14 days after the final dose of ISA101b.

For more information regarding the permitted timing of COVID-19 vaccinations, see Section [8.7.2](#).

3.3.2. Risk-Benefit for Cemiplimab

3.3.2.1. Benefit for Cemiplimab

Cemiplimab is a fully human monoclonal antibody against PD-1 and is currently being evaluated in patients with advanced solid malignancies and B-cell lymphomas whose cancers are incurable and/or have failed to respond to or showed tumor progression despite standard therapy, or patients who are not candidates for standard therapy, or for whom no available therapy is expected to convey clinical benefit. Cemiplimab has demonstrated efficacy (based on ORR and DOR) and is approved in the US for patients with advanced cutaneous squamous cell carcinoma (CSCC), locally advanced basal cell carcinoma, and as a first-line treatment option in advanced non-small cell lung cancer.

As described in earlier sections, antibodies to PD-1/PDL-1 have been shown to be effective therapeutic options for metastatic cervical cancer. Cemiplimab is currently being evaluated in a phase 3 randomized study for survival benefit over chemotherapy. The potential benefit for patients includes increased response rate, longer duration of response, avoidance of risks associated with chemotherapy and increased survival.

3.3.2.2. Risk for Cemiplimab

To mitigate this risk, tumor assessments are performed after every 2 doses of cemiplimab for the first 4 cycles. Subsequent cycles will have tumor assessments after every 3 doses of cemiplimab. Tumor assessments are designed to allow patients to pursue other treatment plans if clinically indicated.

The safety profile of cemiplimab is similar to the safety profile of other anti-PD-1/PD-L1. The important identified risks are immune-mediated adverse events (imAEs) and infusion-related reactions (IRRs). The mitigation strategies for these risks are described in Section [8.2.3.1](#) through Section [8.3.1](#).

More detailed information about the known and expected risks and reasonably expected AEs of cemiplimab may be found in the most recent approved version of the Investigator's Brochures.

3.3.2.3. Benefit:Risk for Cemiplimab

Based on the currently available safety information for cemiplimab, safety information from other anti-PD-1 antibodies, the adequate risk identification and minimization described in the Investigator's Brochure/protocols/informed consent forms (ICFs), the emerging preliminary

activity of cemiplimab on solid malignancies (including CSCC, non-small cell lung cancer [NSCLC] and cervical), the benefit-risk is considered favorable for continued clinical studies in these and other indications.

3.3.3. Risk-Benefit for ISA101b

3.3.3.1. Benefit of ISA101b

ISA101b is designed as a therapeutic vaccine, which targets distinct human pathogenic viral antigens and triggers a highly human-specific immune response. The involved immunostimulatory/ immunomodulatory effects (eg, cascades of involved chemokines/cytokines and cells of the immune system but also organ and target antigen structures), but also the HPV induced effects/target structures are highly human specific.

As described in earlier sections, ISA101b and its precursor have been shown to initiate and/or stimulate an HPV16 specific immune response in patients with HPV16 induced lesions. This was specifically evident in patients with HPV16 metastatic cervical cancer. A pilot study with combination of ISA101b showed an increased response rate and overall survival. Therefore, the potential benefits for patients receiving ISA101b include increased response rate, longer duration of response, avoidance of risks associated with chemotherapy and increased survival.

3.3.3.2. Risk of ISA101b

The fundamental risk is a lack of response. To mitigate this risk, patients will undergo frequent tumor assessments. This will allow patients to pursue other treatment plans.

As with all immunomodulation agents, the TEAEs of interest are local and systemic immune-mediated AEs. Local ISRs are detailed in Section 8.3.1.3. ImAEs and IRRs are detailed in Section 8.2.3 and Section 8.3.1.

More detailed information about the known and expected risks and reasonably expected AEs of ISA101b may be found in the most recent approved version of the Investigator's Brochures.

3.3.3.3. Benefit:Risk for Cemiplimab/ISA101b Combination

The combination of ISA101b and cemiplimab in this study is expected to have a positive benefit-risk profile for the treatment of patients with HPV16 positive cervical cancer. Anti-PD1 inhibitors given as monotherapy have shown activity and a well-established acceptable toxicity profile in recurrent/metastatic cervical cancer patients. ISA101b has been demonstrated to induce a robust and persistent T-cell response in patients with HPV16 driven malignancies, including cervical cancer and OPC. The combination of ISA101b with the anti-PD1 nivolumab achieved higher response rates compared to a historical control of nivolumab alone in the treatment of HPV16 positive OPC, albeit in a small number of patients with heterogeneous prior therapy. Finally, the combination of ISA101 with nivolumab has shown no unexpected toxicities in patients with OPC (Massarelli, 2019).

Since HPV-positive OPC patients with recurrent cancer routinely receive checkpoint inhibitors in first or second-line treatment, the use of cemiplimab as the treatment backbone is acceptable in order to objectively test the hypothesis of improved efficacy with the addition of ISA101b to an anti-PD-1 inhibitor in HPV-driven malignancies.

More detailed information about the known and expected benefits and risks and reasonably expected AEs of cemiplimab and ISA101b may be found in the most recent approved versions of the respective Investigator's Brochures.

4. ENDPOINTS

4.1. Primary Endpoint

The primary endpoint is ORR based on radiographic response, measured by RECIST version 1.1.

4.2. Secondary Endpoints

The secondary endpoints are:

- Incidence and severity of TEAEs/adverse events of special interest (AESIs)/serious adverse events (SAEs) and \geq grade 3 laboratory abnormalities during the treatment period and up to 90 days after the last dose of study treatment
- DOR
- PFS
- OS

4.3. Exploratory Endpoints

The exploratory endpoints are:

- Association of clinical efficacy endpoints with baseline tumor biomarker parameters (PD-L1, immune cell subsets, MHC class I/II, gene expression profile and tumor mutational burden)
- In a subset of study sites: Association of clinical efficacy endpoints with post-treatment changes in frequency and clonal repertoire of HPV antigen specific T cells, peripheral blood immune cell subsets (Teff, Treg, myeloid, dendritic and NK cells) and serum cytokine levels
- Cemiplimab immunogenicity as measured by anti-drug antibodies (ADA) to cemiplimab
- HPV serotyping of archival tumor

5. STUDY VARIABLES

5.1. Demographic and Baseline Characteristics

Baseline characteristics will include standard demography (eg, age, race, weight, height, etc), disease characteristics, medical history, and medication history for each patient.

5.2. Efficacy Variables

Efficacy variables include, but are not limited to, the following:

- Tumor Assessments for Response: CT and/or MRI scan
- ORR with confirmed CR or PR per RECIST 1.1 when evaluating best overall response (BOR)
- DOR
- PFS
- OS

Variables are further defined in Section [11.4](#).

5.3. Safety Variables

Safety variables include, but are not limited to, the incidence and severity of the following:

- TEAEs (Section [10.2.1](#))
- SAEs (see Section [10.2.2](#))
- AESIs (see Section [10.2.3](#))
- ≥ 3 grade laboratory abnormalities (see Section [10.1.3](#))

Variables are further defined in Section [11.4](#).

5.4. Immunogenicity Variables

The immunogenicity variables for cemiplimab are ADA status, titer, and time-point/visit. Samples in this study will be collected at the clinic visits specified in [Table 2](#).

5.5. Pharmacodynamic and Other Biomarker Variables

Pharmacodynamic and biomarker variables are:

- Baseline tumor tissue PD-L1 expression by immunohistochemistry (IHC)
- Baseline tumor tissue density of immune cell subsets (Teff, Treg, myeloid cell, others)
- Changes in peripheral HPV16 E6/E7 specific T cell frequency, clonal repertoire and functional phenotype (cytokine secretion profile, surface marker expression)

- Changes in peripheral blood immune cell subsets (Teff, Treg, myeloid, dendritic and NK cells)
- Changes in systemic inflammatory markers (IFN γ , TNF-alpha, others)
- HPV serotyping of archival tumor

6. STUDY DESIGN

6.1. Study Description and Duration

This will be a single-arm, phase 2, global study of treatment with cemiplimab + ISA101b in HPV16-positive cervical cancer patients with disease progression on first line chemotherapy in the recurrent or metastatic setting. Study treatment and duration include cemiplimab every 3 weeks (with 3 doses of ISA101b on days 1, 29, and 50) until progression or any reason for early discontinuation as outlined in Section 7.3 and Section 8.2.2.

Patients will undergo screening evaluations to determine eligibility within 28 days prior to first treatment. All patients will receive the following regimen:

- ISA101b 100 µg/peptide by SC injection on day 1, day 29, and day 50 (total of 3 doses).
- Cemiplimab 350 mg given by IV infusion over 30 minutes Q3W on days 8 and 29 in cycle 1, on days 1 and 22 in cycles 2 through 4, and on days 1, 22, and 43 in all subsequent cycles or until disease progression or discontinuation of study drug for any other reason.

[figure not shown]
Note: On days 29 and 50, cemiplimab will be administered first, and ISA101b will be administered approximately 1 hour after the end of the cemiplimab infusion. Patients must be observed for 4 hours after each ISA101b administration.

The timing of doses is summarized in Figure 2. Cycle 1 will be 7 weeks long, cycles 2 through 4 will be 6 weeks long, and all subsequent cycles will be 9 weeks long.

Patients will be assessed for response at cycle 1 day 50 (week 7), then once per cycle (every 6 weeks for 3 cycles, then every 9 weeks in all subsequent cycles or until disease progression or discontinuation of study drug for any other reason; Section 8.8, Section 8.2.2, and Section 7.3, respectively). Patients with confirmed CR after a minimum of 48 weeks of treatment may elect to discontinue treatment and continue with all relevant study assessments (eg, efficacy assessments).

There will be a 90-day safety follow-up after the last dose of cemiplimab. Patients who discontinue study drug for reasons other than progression will be followed approximately every 4 months by scans until disease progression or until the patient commences another anticancer systemic therapy, whichever comes first. After progression, survival follow-up should occur approximately every 4 months.

The total duration of study from start of screening to final analysis of OS is expected to be approximately 36 months (approximately 12 months of accrual, approximately 12 months of treatment, and approximately 12 months of follow up).

Figure 2: Study Flow Diagram

¹ Withdrawal due to reasons as listed in Section 7.3 and Section 8.2.2.

End of treatment is defined as the end of study drug. Patients may discontinue study drug for progression of disease or for any reason listed in Section 7.3 and Section 8.2.2. Thirty days after the last dose of study drug, patients will have EOT visit. Ninety days after the last dose of study drug, patients will have the safety follow-up visit (Table 2).

A patient who progresses on treatment will have EOT visit and safety follow-up visit. End of study (EOS) disposition will be on or after the safety follow-up visit. They will then enter survival follow-up.

A patient who discontinues treatment for reasons other than progression, as listed in Section 7.3 and Section 8.2.2, will have EOT and safety follow-up visit. They will then have tumor assessments until progression or the start of another anticancer therapy. At progression or start of another anticancer therapy, patients will have EOS disposition and then enter survival follow-up.

6.1.1. End of Study Definition

The end of the study is defined as the date of the last contact of the last patient of the last investigational site in the study.

6.2. Planned Interim Analysis

There will be no formal interim analysis in this study. Administrative efficacy review may be performed when at least 4 tumor assessments are collected for the first 53 patients.

7. SELECTION, WITHDRAWAL, AND REPLACEMENT OF PATIENTS

7.1. Number of Patients Planned

Approximately 105 patients are planned to be enrolled in the study.

7.2. Study Population

The study population is patients with HPV16 positive cervical cancer with squamous histology (SCC) or adenocarcinoma/adenosquamous (AC) histology who have progressed on first line chemotherapy in the recurrent or metastatic setting. Patients with AC histology will be capped at approximately 20% of total enrollment.

7.2.1. Inclusion Criteria

A patient must meet the following criteria to be eligible for inclusion in the study:

1. Adult patients ≥ 18 years of age (or the legal age of adults to consent to participate in a clinical study per country specific regulations).
2. Has histologically confirmed recurrent or metastatic HPV16 positive cervical cancer as determined by an investigational HPV16 PCR assay by Qiagen, who have experienced disease progression after treatment with platinum containing therapy (must have been used to treat metastatic, persistent, or recurrent cervical cancer). NOTE: Platinum-therapy given in other settings (eg, concurrent with radiation therapy as part of curative-intent therapy, after radiation [or chemoradiation] as adjuvant treatment in a patient with no evidence of disease) does not satisfy the eligibility requirement regarding prior platinum therapy.

Acceptable histology is squamous carcinoma and adenocarcinoma/adenosquamous carcinomas. Sarcomas and neuro-endocrine carcinomas are not eligible histologies.

3. Patient must be determined to be positive for HPV16 genotype, as determined by a specified central reference laboratory.
4. Patient must have measurable disease as defined by RECIST 1.1. Measurable disease is defined as at least 1 lesion that can be accurately measured in at least 1 dimension (longest dimension to be recorded). Each lesion must be ≥ 10 mm when measured by computed tomography (CT), magnetic resonance imaging (MRI), or caliper measurement by clinical exam or must be ≥ 20 mm when measured by chest x-ray. Lymph nodes must be ≥ 15 mm in short axis when measured by CT or MRI. Tumors within a previously irradiated field will be designated as non-measurable lesions unless progression is documented or a biopsy is obtained to confirm persistence at least 90 days following completion of radiation therapy.
5. Patients must meet at least 1 of the following criteria regarding prior bevacizumab therapy:
 - a. Received prior bevacizumab-containing therapy and experienced subsequent progression of disease
 - b. Received prior bevacizumab-containing therapy which was discontinued due to toxicity

- c. Was unsuitable for bevacizumab due to i) unacceptable risk of fistula formation, ii) poorly controlled hypertension, iii) low risk disease according to Moore criteria
- d. Refused prior bevacizumab
- e. Did not have access to bevacizumab

6. Patients must meet at least 1 of the following criteria regarding prior taxol therapy
 - a. Received prior taxol-containing therapy and experienced subsequent progression of disease
 - b. Received prior taxol-containing therapy which was discontinued due to toxicity
 - c. Was unsuitable for taxol therapy due to i) neuropathy, ii) allergy or intolerance to taxol or one of its components
 - d. Refused prior taxol
7. ECOG performance status of 0 or 1.
8. Has adequate organ and bone marrow function documented by:
 - a. Hemoglobin ≥ 8 g/dL
 - b. Absolute neutrophil count $\geq 1.0 \times 10^9/L$
 - c. Platelet count $\geq 75 \times 10^9/L$
 - d. Serum creatinine $\leq 1.5 \times$ upper limit of normal (ULN) or estimated glomerular filtration rate >30 mL/min/1.73m². A 24-hour urine creatinine collection may substitute for the calculated creatinine clearance to meet eligibility criteria.
 - e. Adequate hepatic function:
 - (i) Total bilirubin $\leq 1.5 \times$ ULN ($\leq 3 \times$ ULN if tumor liver involvement)
 - (ii) Aspartate Aminotransferase (AST) $\leq 2.5 \times$ ULN ($\leq 3 \times$ ULN if tumor liver involvement)
 - (iii) Alanine Aminotransferase (ALT) $\leq 2.5 \times$ ULN ($\leq 3 \times$ ULN if tumor liver involvement)
 - (iv) Alkaline Phosphatase (ALP) $\leq 2.5 \times$ ULN ($\leq 3 \times$ ULN if tumor liver or bone involvement)

NOTES:

- In patients with tumor liver involvement if levels of AST $\geq 3 \times$ ULN or ALT $\geq 3 \times$ ULN, and bilirubin levels $\geq 2 \times$ ULN will be excluded regardless of the above criteria
- Patients with Gilbert's syndrome do not need to meet total bilirubin requirements provided their total bilirubin is not greater from their historical level. Gilbert's syndrome must be documented appropriately as past medical history

9. Anticipated life expectancy ≥ 20 weeks.
10. Is willing and able to comply with clinic visits and study-related procedures and requirements
11. Able to understand and complete study-related questionnaires
12. Provide informed consent signed by study patient or legally acceptable representative

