14. Limited physical exam includes lungs, heart, abdomen, and skin.
15. Vital signs are collected within 10 minutes prior to infusion, and approximately 15 minutes (± 10 minutes) after the completion of the infusion. Vital signs will also be taken every hour

during the 4-hour observation after administration of ISA101b. Note: Blood pressure should be measured after the patient has been resting quietly for at least 5 minutes. Blood pressure may be obtained from a seated or recumbent position and should be done consistently throughout the study. When scheduled at the same time as other procedures, vital signs should be measured prior to clinical laboratory assessments, PK, or exploratory sample collection.

16. Hematology and chemistry samples may be obtained ≤ 72 hours prior to cemiplimab treatment.
17. Pre-dose serum or urine β -human chorionic gonadotropin (HCG) up to 72 hours prior to study drug administration. Serum/urine pregnancy tests are requirements for women of child bearing potential only.
18. Serum samples for cemiplimab concentration will be collected from all patients pre-dose (C_{trough}) on cycle 1 day 1 and every other cycle for the first 2 years of treatment. After 2 years, samples for cemiplimab concentration will be collected pre-dose every 6 months (24 weeks) during therapy and at EOT.
19. ADA serum samples for cemiplimab will be collected pre-dose of cemiplimab administration on day 1 of cycle 1, and pre-dose of cemiplimab on day 1 of cycles 3 and 5 for the first year of treatment, then pre-dose every 4 cycles for the subsequent years of treatment (eg, C9, C13 and so on) and at EOT. In the event of AESI, additional samples may be collected for ADA analysis at or near the event when possible.
20. Peripheral blood mononuclear cell (PBMC) collection is optional. PBMC samples will be collected pre-dose on day 1, 8, and 29 of cycle 1, pre-dose on day 1 of cycles 2 through 4, day 1 of cycles 5+, and at end of treatment.
21. Pharmacogenomics (optional sub-study): See Section [9.2.10](#).

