11.1. Statistical Hypothesis

This is a single arm, open label study and there is no formal statistical hypothesis in this study.

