11.2. Justification of Sample Size

The planned total sample size for this study is 105 patients.

The primary objective of the study is to estimate the clinical benefit of cemiplimab + ISA101b after progression on first line chemotherapy, as assessed by objective response rate (ORR). With 105 patients, Table 3 below presents various response rates and associated 2-sided 95% CIs using a normal approximation of the binomial distribution, and precision of estimation defined as distance from the boundary to the center. If observed ORR ranges from 20.0% to 34.3%, the precision estimation using 105 patients ranges from 7.7% to 9.1%.

Table 3: The 2-sided 95% Confidence Intervals for Observed ORR Based on a Sample Size of 105 Patients

Number of Responders	Observed ORR	95% CI	Precision
21	20.0%	(12.4, 27.7)	7.7%
24	22.9%	(14.8, 30.9)	8.0%
27	25.7%	(17.4, 34.1)	8.4%
31	29.5%	(20.8, 38.3)	8.8%
36	34.3%	(25.2, 43.4)	9.1%

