11.4.3.1. Primary Efficacy Analysis

Primary efficacy analysis will be performed when the last patient enrolled has had the opportunity for at least 4 tumor assessments.

The primary endpoint for efficacy analyses is the investigator-assessed ORR as determined by RECIST version 1.1 ([Eisenhauer, 2009](#)). The ORR is defined as the proportion of patients who achieve a best overall response (BOR) of CR or PR. Patients who are not evaluable for BOR will

be considered as non-responders. The ORR along with the 2-sided 95% confidence interval using a normal approximation of the binomial distribution will be summarized.

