1.2.1. Special Considerations

Bone lesions:

- Bone scan, PET scan or plain films are not considered adequate imaging techniques to measure bone lesions. However, these techniques can be used to confirm the presence or disappearance of bone lesions.
- Lytic bone lesions or mixed lytic-blastic lesions, with identifiable soft tissue components, that can be evaluated by cross sectional imaging techniques such as CT

or MRI can be considered measurable lesions if the soft tissue component meets the definition of measurability described above.

- Blastic bone lesions are non-measurable.

Cystic lesions:

Cystic lesions that meet the criteria for radiographically defined simple cysts should not be considered malignant lesions (neither measurable nor nonmeasurable) since they are, by definition, simple cysts. “Cystic lesions” thought to represent cystic metastases can be considered measurable lesions, if they meet the definition of measurability described above. However, if non-cystic lesions are present in the same patient, these are preferred for selection as target lesions.

Lesions with prior local treatment:

- Tumor lesions situated in a previously irradiated area, or in an area subjected to other locoregional therapy, are usually not considered measurable unless there has been demonstrated progression in the lesion.

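### Inclusion criterion 4 defines measurable disease more widely than the CT/MRI response rules and Appendix 3, so a few patients could be misscored for the primary ORR (minor)

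*Protocol*

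**What the plan says.** **Eligibility.** Protocol 7.2.1, criterion 4, asks for measurable disease under RECIST 1.1. It accepts a lesion of at least 10 mm by CT, by MRI "or caliper measurement by clinical exam", or of at least 20 mm by chest x-ray. A tumor in an irradiated field is non-measurable "unless progression is documented or a biopsy is obtained to confirm persistence at least 90 days following completion of radiation therapy". Exclusion 3 in 7.2.2 bars radiation only in the 14 days before first dosing.

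**Response assessment.** Section 4.1 makes the primary endpoint a radiographic ORR. Section 5.2 lists "Tumor Assessments for Response: CT and/or MRI scan". Table 2 and section 9.2.2.1 schedule CT/MRI and no caliper measurement. Footnote 14 to Table 2 says: "Limited physical exam includes lungs, heart, abdomen, and skin"; section 9.2.3.5 adds other organ systems. Neither names a pelvic examination.

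**Measurement rule.** Section 9.2.2.1.1 points to Appendix 3. Its section 1.1 lists CT, MRI and calipers but not chest x-ray, and section 1.2 classes all other lesions as nonmeasurable. Under its section 1.2.1, lesions in an irradiated area "are usually not considered measurable unless there has been demonstrated progression in the lesion"; biopsy is not mentioned.

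**Analysis.** The FAS (Protocol 11.3.1, SAP 3.1) is every enrolled and dosed patient, with no measurable-disease condition. Patients not evaluable for best response stay in the denominator as non-responders (Protocol 11.4.3.1, SAP 6.2).

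**The concern.** Eligibility and scoring should rest on the same definition of a measurable lesion. Here they differ in three ways.

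- **Entry by caliper or chest x-ray alone.** The endpoint is radiographic and no caliper or x-ray follow-up is scheduled. If the qualifying lesion cannot be measured on CT or MRI, the patient has no target lesion on the scheduled assessments.
- **Entry by biopsy-proven persistence in an irradiated field.** One site, reading criterion 4, would make this a target lesion. Another, reading Appendix 3, could make it non-target. Partial response is defined on the sum of target lesions (Appendix 3, 1.5.1), so the score of a patient with no other measurable lesion could depend on which page was read.
- **Timing of progression.** The 90-day condition is attached to the biopsy clause. Nothing is clearly attached to the progression clause, so a lesion irradiated because it had progressed could be chosen as a target and then shrink from the radiation.

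The first two pull ORR down and the third pushes it up. There is no control arm to absorb either, and the confidence interval does not cover this kind of error.

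**Working it through.** **1. The plan's own figure.** "The planned total sample size for this study is 105 patients" (Protocol 11.2), and the interval is specified as "2-sided 95% confidence interval using a normal approximation of the binomial distribution will be summarized" (11.4.3.1). The half-width is 1.96 × √(p(1 − p)/105):

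- 21/105 = 20.0%: 1.96 × √(0.2000 × 0.8000/105) = 7.65 points (stated 7.7)
- 27/105 = 25.7%: 1.96 × √(0.2571 × 0.7429/105) = 8.36 points (stated 8.4)
- 36/105 = 34.3%: 1.96 × √(0.3429 × 0.6571/105) = 9.08 points (stated 9.1)

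All five rows of Table 3 reproduce to within 0.1 point. No stated figure is in question.

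**2. Downward shift.** Let k of 105 patients be unable to score CR or PR on CT/MRI and count as non-responders. Expected ORR is p × (105 − k)/105, a fall of p × k/105. The documents give no k; 1 to 5 is an assumption.

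| True ORR | k = 1 | k = 3 | k = 5 |
|---|---|---|---|
| 20.0% | 19.8% (−0.2) | 19.4% (−0.6) | 19.0% (−1.0) |
| 25.7% | 25.5% (−0.2) | 25.0% (−0.7) | 24.5% (−1.2) |
| 34.3% | 34.0% (−0.3) | 33.3% (−1.0) | 32.7% (−1.6) |

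As a stress case, k = 21 (20% of patients) lowers the three rates by 4.0, 5.1 and 6.9 points. At 25.7%, the fall equals the half-width only when k = 105 × 8.36/25.7, about 34 patients.

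**3. Upward shift.** Each radiation response counted where treatment would have produced none adds 1/105 = 0.95 point. Five would add 5/105 = 4.8 points.

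**4. Is the timing possible?** Screening runs from day −28 to day −1 (Table 2), and Appendix 3, 1.3, allows baseline evaluation up to 4 weeks before treatment. Radiation is barred only within 14 days of dosing. A scan on day −28 followed by radiation between about day −27 and day −15 breaks neither limit. If no later scan is taken, the day −28 scan is the baseline under SAP 6.1.

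**5. The routes side by side.**

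| Route in criterion 4 | Appendix 3 | Scheduled CT/MRI assessment |
|---|---|---|
| Caliper, 10 mm | Measurable (1.1); clinical follow-up allowed if the lesion cannot be imaged (1.3) | No caliper visit scheduled |
| Chest x-ray, 20 mm | Not listed (1.1, 1.2) | Chest imaging mandatory (9.2.2.1) |
| In-field, progression | Listed (1.2.1); timing not stated | Measurable on CT/MRI |
| In-field, biopsy persistence | Not mentioned (1.2.1, with the qualifier usually) | May be measurable on CT/MRI |

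**The case against.** Much of the protocol limits the damage.

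- **Caliper lesions.** A reader might infer that they are never remeasured and that these patients cannot be scored validly. The documents do not support that. Appendix 3 counts caliper lesions as measurable, asks for the same method at baseline and follow-up, and allows clinical examination when a lesion cannot be imaged. Section 9.2.2.1 requires imaging of chest, abdomen, pelvis and every other known site, so many palpable lesions will also be on a scan. The list in section 5.2 is not exhaustive. What stands is that no caliper measurement is scheduled and the endpoint is called radiographic.
- **Chest x-ray.** A lesion visible on chest x-ray lies in a region that must be imaged anyway, so this mismatch is clear in wording but probably rare in effect.
- **Biopsy persistence.** A reader might infer that these patients are automatic non-responders. The word usually in Appendix 3 leaves room for a protocol exception, and criterion 4 may be that exception. Such a lesion can be measured on CT/MRI, and Appendix 3, 1.5.2, defines complete response even for non-target disease. What stands is that nothing says criterion 4 is the exception.
- **Timing.** Progression after radiation is the more natural reading of both passages, and Appendix 3, 1.3, asks for baseline evaluation as close as possible to treatment. What stands is that the order is not stated and the screening window permits the other sequence.
- **Size.** Protocol 11.1 says "there is no formal statistical hypothesis in this study", so no decision threshold can be crossed, and counting non-evaluable patients as non-responders is prespecified.

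**Conclusion.** The mismatch is real and its expected effect is small. Criterion 4 admits patients by routes that the scheduled assessments or Appendix 3 do not mirror, and it leaves the order of radiation, progression and baseline scan open. With an assumed 1 to 5 unscorable patients, ORR falls by about 0.2 to 1.2 points at a true 25.7%. Each misattributed radiation response adds 0.95 point. Both are small against the planned half-width of 7.7 to 9.1 points, and they run in opposite directions.

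The result rests on two assumptions: the number of affected patients, which the documents do not give, and that none of the unscorable patients reaches CR or PR, which overstates the downward shift. The documents do not show that any patient will be misscored, and Table 3 is unaffected. This is a minor point, worth correcting because the error is avoidable and falls on the only primary estimate of a single-arm trial.

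**What to change.** 1. In criterion 4, require at least one lesion measurable by CT or MRI at baseline. A caliper or chest x-ray measurement alone should not be sufficient.
2. State that progression of an in-field lesion must be documented after the end of that lesion's last radiation, and that its baseline scan must also follow that radiation.
3. Reconcile criterion 4 with Appendix 3, 1.2.1, so that the same rule on biopsy-proven persistence appears in both. Whether such lesions may be targets is a choice for the sponsor; the need is for one rule.

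The cost is protocol wording and a few patients with examination-only disease becoming ineligible. Table 3 and the planned analysis stay as they are.
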